### **Sample Size and Population**

The setting of this study is all four county hospitals that anchor care for patients in the Los Angeles County public healthcare system (LAC), which serves the largest, most ethnically diverse county in the United States. This system, often called the Safety Net, serves more than 10 million residents and provides healthcare to 700,000 people every year, and treats more than 300,000 emergency and trauma victims every year. Through an integrated network of hospitals, health centers and clinics, the LA County Health Services System makes medical and preventive care services accessible in communities across the county. According to LAC administrative databases, more than 50% of patients use a language other than English as their primary language and 63% of outpatients are uninsured.

A total of 500 subjects with the onset of ischemic stroke, hemorrhagic stroke, or transient ischemic attack (TIA) within the prior three months will be recruited from the following off-campus locations:

- (1) Los Angeles County Hospital + USC Medical Center (LAC+USC),
- (2) Rancho Los Amigos National Rehabilitation Center (Rancho Los Amigos),
- (3) Olive View-UCLA, and
- (4) Harbor-UCLA Medical Center.

No subjects will be recruited at UCLA.

Stratification variables are as follows, with 24 strata:

- Site (4 sites)
- Language (3: English, Spanish, other)
- Type of Stroke (2: ischemic/TIA, hemorrhagic)

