### 9.3 Sample Size and Accrual

#### **Power Analysis**

Power Analyses was conducted with comparison of main outcomes (systolic blood pressure (SBP)) between the control and intervention arms. Based on availability of patients and our capacity, we plan to enroll 500 subjects from four senior centers. Using Intra-class correlation (ICC) of the four centers at 0.0085 level, attrition after the baseline between 20% to 30% level, mean SBP 141 mm Hg and standard deviation (SD) 20, three repeated measurements: baseline, 3 months, and 12 months (Brown and Prescott 2006), the underlying

statistical power of the study comes from two dimensions of observations: the number of unique subjects and the number of repeated measurements within a subject. Based on sample size and power analyses method proposed by Diggle et al. (1994) and Liu et al. (2005) for repeated measures analysis with a type I error of 0.05, type II error of 0.2 (or equivalent to power of 80%), 2.6 and 2.4 average data points for each subject (corresponding to 20% and 30% attrition respectively), and an auto-correlation at 0.2 level, the effective sample size will be 147 and 147 out of the planned 250 and 250 participants in each of the 2 arms (after adjusting for clustering effect), which will enable us to detect an effect size for SBP as small as 0.215 in standard deviation units or 4.29 mm Hg (for 20% attrition), and 0.253 in standard deviation units or 5.06 mm Hg (for 30% attrition).

The seminal work for moderator and mediator effect was from Baron and Kenny (1986). For potential moderators (e.g., age, gender, stroke type and severity, education, country of birth/primary language), we will test power of moderation using the most common measure of effect size  $f^2$  (Aiken & West, 2001), which equals the unique variance explained by the interaction term divided by sum of the error and interaction variances. Cohen (1988) has suggested that  $f^2$  effect sizes of 0.02, 0.15, and 0.35 are termed small, medium, and large, respectively. A more realistic standard for effect sizes with moderators might be 0.005, 0.01, and 0.025 for small, medium, and large, respectively.

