To check the fidelity (uptake) of the SUCCEED intervention, we will also analyze attendance at SUCCEED clinics and the number of telephone coordination of care calls made during enrollment. Because subjects will be recruited from four hospital systems, there could be some underlying intra-site correlations of outcome measures in the collected data, which will have potential impacts on statistical significant tests of parameter estimates in the analyses. To take this into account in our analyses and modeling, robust standard errors will be calculated using Huber/ White/Sandwich method to ensure valid significance testing. Although we will assess for the impact of clustering data structure, we do not expect a large intra-site correlation because the three sites are part of the same county healthcare system and we are not aware of differences of outcomes by site. Furthermore, we will also include site dummies in our model to control and evaluate the differences in parameter estimates, especially if there are significant variations among the sites.

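### Section 9.5 names no cluster unit for its sandwich errors; read as clustered on the four sites, type I error is about 15–20% with a normal reference, or 12-month power at 8 mm Hg falls from about 98% to 76–80% with t(3) (400 completers)

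*Combined protocol and SAP*

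**What the plan says.** Section 9.5 gives the problem first: "Because subjects will be recruited from four hospital systems, there could be some underlying intra-site correlations of outcome measures". The remedy follows: "robust standard errors will be calculated using Huber/ White/Sandwich method to ensure valid significance testing". It then says "Although we will assess for the impact of clustering data structure, we do not expect a large intra-site correlation", and adds "we will also include site dummies in our model to control and evaluate the differences in parameter estimates". No cluster unit, small-sample correction, degrees of freedom or reference distribution is given. The regressions are to carry an enrollment and attrition weight. They will be run with and without covariates, and neither version is named as primary.

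Section 9.3 also treats site as a source of clustering: "Using Intra-class correlation (ICC) of the four centers at 0.0085 level". It plans a type I error of 0.05, 80% power and "three repeated measurements: baseline, 3 months, and 12 months". At 20% attrition it claims an "effect size for SBP as small as 0.215 in standard deviation units or 4.29 mm Hg", and at 30% attrition 5.06 mm Hg. Section 1.1 (Objective #2) hypothesises an 8 mm Hg difference at 1 year. Sections 4.3.4 and 9.1 describe individual 1:1 randomisation, stratified by site, language and stroke type.

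**The concern.** A sandwich estimator allows for correlation within site only if residual contributions are summed by site. A heteroskedasticity-robust estimator at patient level does not address it. An analyst who follows the stated purpose would therefore cluster on site, with four clusters. The estimator's large-sample justification rests on the number of clusters, not the number of patients, and four is far too few for a normal reference. A t reference on 3 degrees of freedom repairs the size but costs power.

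The arm contrast does not need site clustering. Both arms are randomised within each site, the planned dummies absorb site differences, and the Synopsis says "The setting of this study is all four county hospitals that anchor care for patients", so the sites are not a sample from a larger set. Because the candidate tests differ so much in size and power, the choice should not be left until results are visible.

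**Working it through.** **Inputs.** From Section 9.3: SD 20, site ICC 0.0085, correlation 0.2, alpha 0.05 (two-sided assumed), 500 enrolled, 20–30% attrition (400 or 350 completers). From Section 1.1: 8 mm Hg. Completers per site are not stated. Assumed: equal sites; the 2011 shares in Table 2 of Section 2.1 (366/165/206/351 of 1088); and a skewed case.

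**1. The plan's own figure.** With 147 per arm, (1.960 + 0.842) × √(2/147) = 0.327 SD. Multiplying by √[(1 + (m − 1) × 0.2)/m] gives 0.233 SD for m = 2.6 and 0.239 SD for m = 2.4. The plan states 0.215 and 0.253. The figures do not reproduce, but nothing below depends on them.

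**2. Patient-level power at 8 mm Hg.** With 200 per arm, SE = 20 × √(2/200) = 2.0, the ratio is 8/2.0 = 4.0, and power = Φ(4.0 − 1.96) = 97.9%. With 175 per arm the ratio is 3.742 and power 96.3%.

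**3. Four equal sites, analytic.** The estimate is the mean of four within-site differences, and the corrected clustered variance is essentially their sample variance over 4, so the statistic follows t(3).
- Normal reference, corrected: P(|t3| > 1.96) = 14.5%.
- Normal reference, uncorrected: P(|t3| > 1.96 × √(3/4)) = 18.8%.
- t(3) reference, critical value 3.182: noncentral t power is 75.5% at noncentrality 4.0 and 70.4% at 3.742.

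The site effect cancels from each within-site difference, so the ICC hardly matters.

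**4. Simulation of the 12-month model** (site dummies, unweighted, 40,000 replicates). The first four result columns are type I error; the last two are power at 8 mm Hg.

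| Completers by site | Site, normal, uncorrected | Site, normal, corrected | Site, t(3), corrected | Patient-level HC1 | Power: site t(3) | Power: patient-level |
|---|---|---|---|---|---|---|
| 100 each | 18.5% | 14.0% | 4.8% | 4.9% | 75.5% | 98.0% |
| 135/61/76/128 | 19.7% | 15.1% | 5.3% | 5.0% | 76.7% | 97.9% |
| 200/80/70/50 | 21.3% | 16.7% | 6.1% | 5.0% | 79.7% | 97.9% |
| 118/53/66/113 | 19.7% | 15.1% | 5.4% | 5.1% | 71.7% | 96.3% |

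Raising the ICC to 0.05 leaves the normal-reference error at 15.4–19.8%. The uncorrected sandwich with t(3) has 84–85% power at 400 completers (equal or Table 2 sites), but 7–8% type I error. A separate simulation (10,000 replicates) that also adjusted for baseline SBP, language and stroke type gave 77.8% against 98.0% at 400 and 72.7% against 96.9% at 350. HC1 and HC3 both gave 98.0% at 400.

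**5. Stacked 3- and 12-month visits** (10,000 replicates, equal effect at both visits assumed), patient-clustered against site-clustered t(3):
- 8 mm Hg: 100% against 93.7% (400); 99.9% against 90.4% (350).
- 4.29 mm Hg (400): 82.3% against 52.2%.
- 5.06 mm Hg (350): 88.5% against 58.1%.

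**6. Baseline adjustment at r = 0.2**, in units of SD²: change score 2(1 − r) = 1.60; follow-up SBP alone 1.00; adjusted for baseline 1 − r² = 0.96. The reduction is 40% against an unadjusted change score and 4% against follow-up SBP alone.

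**7. Shared care teams.** The number of teams and the team ICC are assumptions. With 400 completers, Table 2 shares, HC1 errors and correlation in the intervention arm only, type I error at team ICC 0.0085, 0.02 and 0.05 is 7.3%, 11.3% and 20.8% for four teams, and 6.3%, 8.0% and 12.9% for eight.

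**The case against.** The strongest reply is that the plan never says the errors are clustered on site. That stands. A reader might infer that the primary test will reject a true null 15–20% of the time; the documents do not support this, because patient-level robust errors also fit the named method and give a sound test. The two harms are also alternatives: inflated size with a normal reference, or lost power with t(3).

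A reader might also infer that the trial is underpowered for 8 mm Hg. That does not follow either. Section 9.3 sizes the trial on repeated measures, and stacking the visits leaves 90–94% even with site-clustered t(3). In the 12-month model, 76–80% at 400 completers is close to the 80% target.

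It may be said that Section 9.5 expects little intra-site correlation. That is no defence, since the inflation comes from the number of clusters.

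The best argument against simply switching to patient-level errors is the delivery of the intervention by shared care managers, community health workers and group sessions (Sections 1.1 and 5.1). Outcomes may then be correlated within teams in the intervention arm, so patient-level errors are not free of problems. This stands as a caveat, of a size that the documents do not allow one to fix.

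The covariate point is secondary. Section 9.5 already plans adjusted and unadjusted analyses, and language and stroke type were simulated without any effect on SBP, so no gain from adding them has been shown.

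**Conclusion.** The concern holds as a consequential ambiguity that should be fixed, not as a proven error. On the reading that the stated purpose implies, the options are a test with roughly three to four times the planned type I error, or a valid one that gives up about 18–22 percentage points of 12-month power at 8 mm Hg with 400 completers, and about 24–25 points with 350. At the plan's own detectable effects, stacked-visit power would be 52% and 58%. Patient-level errors avoid this if patients are independent within site and the effect is common to all sites.

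The figures rest on assumed site sizes and on unweighted models of SBP. The documents give no weight distribution, and the outcome of BP under 120/80 was not checked.

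**What to change.** In Section 9.5, state that the robust errors are at patient level, clustered on patient if visits are stacked, and are not clustered on the four sites. State that site is handled by the planned dummies, because randomisation is individual and stratified by site. Give the reference distribution. Keep robust rather than model-based errors while the weights are in the model; HC1 or HC3 will serve equally well.

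Name one primary SBP model, adjusted for baseline SBP, site, language and stroke type, and report other covariate sets as sensitivity analyses. Add a sensitivity analysis that allows for correlation within care teams in the intervention arm.

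The cost is wording. The covariates are already collected and use 3 + 1 + 2 + 1 = 7 degrees of freedom out of 350–400 patients. The care-team analysis needs the team serving each intervention patient to be recorded. The remaining downside is that the primary test itself will not cover team correlation, which could put its type I error at about 6–11% for team ICCs of 0.0085–0.02, and higher if the ICC is larger.

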#### 4.3.4 *Procedure for obtaining intervention group assignment*

Before the RCT begins, we will use computer-assisted stratified randomization of block size of 4. The three stratification variables will be site, spoken language (Spanish, English or other), and type of stroke (ischemic or hemorrhagic). These lists have an allocation ratio of 1:1 of control and intervention. Permuted block randomization that stratifies by site will be used to promote periodic balance through the trial and group balance at the end of the trial. The study programmer/analyst will generate 24 lists, one for each stratum. Each row of the list will include a unique subject IDs and intervention arm of the study. The lists will be kept in a notebook that the Project Coordinator will possess at all times.

For patients who consent to the study and meet inclusion criteria, the RA will collect baseline data (described below in section of Outcome Measures) before randomization so that the RA will collect data uniformly regardless of the eventual allocation of the subject. After an eligible participant has consented and completed the baseline survey, the RA will inform the Project Coordinator with the information needed to choose which of the 24 lists to use. The Project Coordinator will find the next uncrossed row, tell the RA the unique subject ID and intervention assignment, then cross out that row so that the next row will be used when this list is used again.

The Project Coordinator will assign the newly enrolled participant a unique subject ID and inform the RA the assigned randomization status of this subject. The Project Coordinator will mark down in the notebook the date of randomization for that subject ID.

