## 9 STATISTICAL CONSIDERATIONS

### 9.1 General Design Issues

The primary and secondary hypotheses is that subjects randomized to the intervention arm will have better control of risk factors and higher rates of adoption of healthy lifestyle habits compared to the control arm.

All outcomes will be collected by a blinded RA. Vascular events will be collected by patient self-report and will not require an adjudication committee.

The design is a RCT, 1:1 allocation to control and intervention arms. There is no crossover.

Randomization is stratified by site (4), language (3: English, Spanish, other), and type of stroke (2: ischemic/TIA, hemorrhagic). There are 24 strata.

Intervention on period is up to 12 months for persons. It may be discontinued if subjects optimally control risk factors.

After the 12 month study period, subjects will be monitored by telephone for the presence of vascular events and mortality. There is no face-to-face contact, and thus, no collection of SBP, the primary endpoint. This surveillance is to better determine the impact of the intervention in the first 12 months after randomization.

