#### **9.5 Data Analyses**

Baseline characteristics between the SUCCEED intervention and usual care groups will be compared. Continuous variable means will be compared using the t-test and ordinal or non Gaussian continuous variables will be compared using the Wilcoxon rank sum test. Unordered categorical variables will be compared using Chi-square test or Fisher's exact test.

Enrollment weights based on a logistic regression model will be calculated using demographic data collected from eligible non-participants. If needed, attrition weights will be determined from logistic regression models using demographic data on participants who drop out of the study. These two weights will be combined to form an overall weight (using the inverse of the product of the probabilities of participation). Both raw and adjusted rates using the overall weight will be compared between SUCCEED and usual care arms.

Intention to treat analyses on all primary and secondary outcomes will be conducted using ordinal logistic or multiple linear regression models, incorporating the overall weight. Intervention status will be an independent variable in all models. We will compare study outcomes between the control and intervention groups both with and without adjusting for potential covariates associated with the outcome measure.

We will test the moderator and mediator effects separately. To assess the moderating effects, we will compare regression models we fit including interaction terms between the independent variables and each possible effect modifier, and the models that do not include the corresponding interaction terms, using the likelihood ratio test (LRT). To assess the mediating effects, we will use Baron and Kenny (1986) methods to run a series of regression analysis and use the Sobel test and Bootstrapping to test mediating effects.

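### Language and stroke type are stratification factors but are not pre-specified in the main model; if they predict SBP beyond site, the linear-model standard error is modestly conservative

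*Combined protocol and SAP*

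**What the plan says.** **Design.** Section 4.3.4 describes "computer-assisted stratified randomization of block size of 4" and lists the factors: "The three stratification variables will be site, spoken language (Spanish, English or other), and type of stroke (ischemic or hemorrhagic". Section 9.1 repeats this with the number of levels, "Randomization is stratified by site (4), language (3: English, Spanish, other), and type of stroke (2: ischemic/TIA, hemorrhagic", and adds "There are 24 strata". Allocation is "1:1 allocation to control and intervention arms".

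**Analysis.** Section 9.5 is the only description of the models. Outcomes are analysed by "ordinal logistic or multiple linear regression models, incorporating the overall weight", and the arms are compared "both with and without adjusting for potential covariates associated with the outcome measure". Those covariates are not listed, and neither comparison is called primary. The one stratification factor named for the main model is site: "we will also include site dummies in our model to control and evaluate the differences in parameter estimates, especially if there are significant variations". Standard errors are to be of the Huber/White sandwich type.

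**Elsewhere.** Objective 2 in section 1.1 and the power section (9.3) list stroke type and primary language among the potential moderators. Section 9.5 tests moderators separately, through interaction models.

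**The concern.** Blocking within strata makes the arms nearly equal in language mix and stroke-type mix. If those factors predict SBP, the true sampling variance of the treatment difference falls. A model that leaves them out keeps their variance in the residual, so its estimated standard error does not fall with it. The interval is then wider than it need be and the test is conservative.

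The second issue is pre-specification. Because covariates are to be those associated with the outcome, and two versions of the comparison are planned without a ranking, the primary analysis stays open until the data are seen. Fixing the design factors in advance closes part of that choice.

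**Working it through.** **1. The plan's own figure.** Section 9.3 states an effective sample size of 147 per arm and detectable SBP differences of 4.29 mm Hg (20% attrition) and 5.06 mm Hg (30% attrition). Inputs: 250 per arm, ICC 0.0085, SD 20, autocorrelation ρ = 0.2, k = 2.6 or 2.4 data points per subject, power 80%, α = 0.05 (two-sided assumed).

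- 250 / (1 + (m − 1) × 0.0085) gives 147.1 for m = 83.3 (three clusters per arm). It gives 164.2 for m = 62.5 and 121.7 for m = 125.
- From n = 147, the difference (1.960 + 0.842) × 20 × √[2(1 + (k − 1)ρ)/(kn)] is 4.66 mm Hg for k = 2.6 and 4.77 mm Hg for k = 2.4.

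So 4.29 and 5.06 are not reproduced. That is a separate matter. The power section has no term for stratification factors, so 4.29 serves below only as a yardstick for relative change.

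**2. Effect of omitting language and stroke type.** Let R² be the share of SBP variance that the two factors explain beyond site. The documents do not give it, so a range is assumed. For a linear model:

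- SE ratio (site only versus all three factors) = 1/√(1 − R²)
- actual type I error of the site-only test = 2[1 − Φ(1.96/√(1 − R²))]
- detectable difference with all three factors = 4.29 × √(1 − R²)
- power at 4.29 mm Hg with all three factors = Φ(2.802/√(1 − R²) − 1.960)

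| Assumed R² | SE ratio | Type I error, site only | 4.29 mm Hg becomes | Power at 4.29 |
|---|---|---|---|---|
| 0% | 1.000 | 5.0% | 4.29 | 80.0% |
| 1% | 1.005 | 4.9% | 4.27 | 80.4% |
| 2.5% | 1.013 | 4.7% | 4.24 | 81.0% |
| 5% | 1.026 | 4.4% | 4.18 | 82.0% |
| 10% | 1.054 | 3.9% | 4.07 | 84.0% |

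**3. Simulation check.** Each scenario had 4,000 runs with N = 500, blocks of 4 in 24 strata, 25% attrition, SD 20 and an individual-level robust SE. The language mix (45/45/10) and the SBP differences between groups are assumptions.

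| Difference by language and by stroke type | R² | SE, site only | SE, all three | Ratio | Type I error, site only vs all three |
|---|---|---|---|---|---|
| 0 mm Hg | 0% | 2.068 | 2.071 | 0.999 | 5.3% vs 5.4% |
| 5 mm Hg | 2.5% | 2.068 | 2.045 | 1.011 | 4.8% vs 5.1% |
| 10 mm Hg | 9.9% | 2.068 | 1.965 | 1.052 | 4.1% vs 5.3% |

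The Monte Carlo standard error of a 5% rate is √(0.05 × 0.95/4000) = 0.34 percentage points. The simulation agrees with the formula. It also shows that an individual-level robust SE does not remove the conservatism, and that adding the factors costs essentially nothing when they do not matter.

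**4. Power at the hypothesised 8 mm Hg.** On the plan's inputs with n = 147, the SE is 1.66 mm Hg (k = 2.6) or 1.70 mm Hg (k = 2.4). Power is Φ(8/1.66 − 1.96) or Φ(8/1.70 − 1.96), above 99% in both cases. With the simulated single-measurement SEs in the 10 mm Hg scenario, it is 97.2% (2.068) versus 98.3% (1.965).

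**The case against.** The strongest defence is that the plan does not shut these factors out. An adjusted comparison is planned. If language or stroke type predicts SBP, it qualifies as a covariate; if it does not, leaving it out costs nothing. Both are also listed as moderators. A reader might infer from the reference to site alone that language and stroke type are ignored, and the documents do not support that. What stands is that nothing commits either factor to the main model, that no version is primary, and that the separate moderator models are not the primary treatment comparison.

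A reader might also conclude that the SBP standard error is too large as a matter of fact. That too is unsupported:

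- It requires prognostic value beyond site, for which the documents give no figure. An R² near 10% needed 10 mm Hg differences by both factors in the simulation, more than the hypothesised treatment effect.
- The net direction cannot be settled. The calculation is unweighted, whereas the plan uses enrolment and attrition weights. A sandwich estimator clustered on only four sites would tend to give an SE that is too small.
- Site dummies are promised; the hedge in that sentence adds emphasis and does not withdraw the commitment. The relevant R² is therefore the part beyond site.

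Nor is a power loss shown for every outcome. The power section claims no gain from stratification, so nothing promised is lost. The formula is for linear models. In logistic models, such as for the proportion under 120/80, adjustment changes the odds ratio being estimated and generally does not shrink its standard error.

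**Conclusion.** The point holds as a pre-specification gap with a conditional and modest precision cost. Three factors define the randomisation, and one is committed to the main model. For SBP in a linear model, omitting the other two makes the standard error about 0.5% to 5.4% too large over an assumed additional R² of 1% to 10%, with no effect at R² = 0. The lower part of that range is the more plausible. The treatment estimate is not biased, type I error falls below 5% and does not rise above it, and power at 8 mm Hg hardly moves. The gain would be noticeable only for effects near the 4 to 5 mm Hg that the power section treats as detectable. These figures assume a two-sided test, no weights, and a model-based or individual-level robust standard error. The point is a free improvement, not an error that threatens the primary conclusion.

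**What to change.** In section 9.5, state that the primary SBP model includes site (4 levels), language (3) and stroke type (2), as recorded at randomisation, as fixed effects, whatever their significance. That is 3 + 2 + 1 = 6 df, small against 500 planned participants. Name this as the primary comparison and label the unadjusted one as supportive. Use the same terms in the secondary models where event counts allow. For logistic outcomes, naming the covariates also fixes which odds ratio is estimated.

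The cost is one or two sentences. The factors are known for every participant before allocation, because the Project Coordinator needs them to choose the randomisation list, so no new data are required. If the factors turn out not to be prognostic, the simulated SE ratio of 0.999 shows practically no penalty.
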